11.3.3 Safety Populations

The Safety population will include all patients who are randomized and received study product.

11.4 Baseline Comparability

Baseline characteristics will be evaluated separately for the PP, mITT and Safety populations.

The following baseline demographics (determined from their initial study visit) will be evaluated:

- Age (years)
- Sex (Male/Female)
- Ethnicity (Hispanic/Non-Hispanic)
- Race (White, Black/African American, Native Hawaiian or Other Pacific Islander, Asian, American Indian or Alaska Native)
- Type of infection (interdigital only or interdigital with extension)
- Total baseline signs and symptoms score
- Presence or absence of onychomycosis
- Number of infections in the past 12 months
- Primary infective organism

Summary tables by treatment group will be presented. Continuous variables will be summarized using descriptive statistics (number of observations, median, minimum, maximum, mean, and standard deviation). Categorical variables will be summarized using frequencies and percentage. Baseline treatment comparisons will be presented using Chi-Square or Cochran-Mantel-Haenszel (CMH) tests for the categorical variables, and Analysis of Variance for the continuous variables.

All data will be listed by treatment and patient.

11.5 Efficacy Variables

The primary and secondary efficacy variables are the outcome of the KOH test (negative or positive), outcome of the mycological culture (negative or positive), and signs and symptoms scores.

CONFIDENTIAL PROTOCOL

A Randomized, Double-Blind, Vehicle-Controlled, Parallel-Design, Multiple-Site Clinical Study to Evaluate the Therapeutic Equivalence of Ketoconazole Cream 2% (Encube Ethicals Pvt Ltd) to Ketoconazole Cream 2% (G&W Laboratories Inc.) in the Treatment of Tinea Pedis

11.6 Efficacy Endpoints

Primary Efficacy Endpoint

The primary efficacy endpoint is the proportion of patients in each treatment group with a Therapeutic Cure of tinea pedis at the test-of-cure visit two weeks after the end of treatment (Day 56 ± 4).

Secondary Efficacy Endpoints

The secondary efficacy endpoints are:

- The proportion of patients in each treatment group with a Clinical Cure at Day 56 ± 4.
- The proportion of patients in each treatment group with a Mycological Cure at Day 56 ± 4.

Definitions

1. **Therapeutic Cure**: To be considered a Therapeutic Cure, the patient must have both Clinical and Mycological Cure of tinea pedis.
2. **Therapeutic Failure**: A patient will be considered a Therapeutic Failure if:
 - a. the patient is a Clinical or Mycological Failure
 - b. the patient was considered to have an insufficient therapeutic response
 - c. the patient used topical drug therapy for irritation or pruritus on the feet after the treatment phase of the study
3. **Clinical Cure**: To be considered a clinical cure the patient's total severity score must be ≤ 2 with no individual severity score > 1 .
4. **Clinical Failure**: A patient will be considered a Clinical Failure if the patient's total severity score is > 2 or any individual score is > 1 .
5. **Mycological Cure**: To be considered a mycological cure the patient must have a negative KOH test and a negative fungal culture.
6. **Mycological Failure**: A patient will be considered a Mycological Failure if the patient's KOH test is positive or the patient's fungal culture is positive.

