10.3.3 Restrictions During the Study

The following concomitant medications will not be allowed while enrolled in the study:

- Any topical products applied to the treatment area
- Any systemic (e.g., oral or injectable) antibiotics or anti-fungals
- Systemic corticosteroids or immunosuppressive drugs.
- Anti-pruritics, including antihistamines, within 24 hours of study visits.

Patients will be instructed not to use any occlusive wrappings or dressings over the treatment area during the study.

The use of hormonal contraceptives should not be initiated or changed during the study.

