10.6.5 Review and Assessment of Concomitant Medications

At Visit 1, patients will be questioned about medication use over the previous six months. At all subsequent visits, patients will be questioned about ongoing or new concomitant medication use.

CONFIDENTIAL PROTOCOL

A Randomized, Double-Blind, Vehicle-Controlled, Parallel-Design, Multiple-Site Clinical Study to Evaluate the Therapeutic Equivalence of Ketoconazole Cream 2% (Encube Ethicals Pvt Ltd) to Ketoconazole Cream 2% (G&W Laboratories Inc.) in the Treatment of Tinea Pedis

At Visit 2, any patient who has used medications restricted by the protocol may be discontinued from the study. If discontinued, all end of study procedures (Visit 3 procedures) should be performed.

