6. EFFICACY VARIABLES AND EFFICACY ENDPOINTS

Efficacy Variables

The primary and secondary efficacy variables are the outcome of the KOH test (negative or positive), outcome of the mycological culture (negative or positive), and signs and symptoms scores.

Primary Efficacy Endpoint:

The primary efficacy endpoint is the proportion of patients in each treatment group with a Therapeutic Cure of tinea pedis at the test-of-cure visit two weeks after the end of treatment (Day 56 ± 4).

Secondary Efficacy Endpoints:

The secondary efficacy endpoints are:

- The proportion of patients in each treatment group with a Clinical Cure at Day 56 ± 4 .
- The proportion of patients in each treatment group with a Mycological Cure at Day 56 ± 4 .

Definitions

1. **Therapeutic Cure:** To be considered a Therapeutic Cure, the patient must have both Clinical and Mycological Cure of tinea pedis.
2. **Therapeutic Failure:** A patient will be considered a Therapeutic Failure if:

NOVUM PHARMACEUTICAL RESEARCH SERVICES
STATISTICAL ANALYSIS PLAN

Ketoconazole Cream 2%

Protocol / Study No. 71875502

- a. the patient is a Clinical or Mycological Failure
- b. the patient was considered to have an insufficient therapeutic response
- c. the patient used topical drug therapy for irritation or pruritus on the feet between Visit 2 (Day 42 ± 4 days) and Visit 3 (Day 56 ± 4 days)
3. **Clinical Cure:** To be considered a clinical cure the patient's total severity score must be ≤ 2 with no individual severity score > 1 .
4. **Clinical Failure:** A patient will be considered a Clinical Failure if the patient's total severity score is > 2 or any individual score is > 1 .
5. **Mycological Cure:** To be considered a mycological cure the patient must have a negative KOH test and a negative fungal culture.
6. **Mycological Failure:** A patient will be considered a Mycological Failure if the patient's KOH test is positive or the patient's fungal culture is positive.

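### No rule fails an mITT patient who stays in the study after using a prohibited antifungal: if clear at Visit 3, that patient is scored a Therapeutic Cure

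*Protocol*

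**What the plan says.** - **Prohibition.** Protocol 10.3.3 bars "Any topical products applied to the treatment area" and "Any systemic (e.g., oral or injectable) antibiotics or anti-fungals" while a patient is enrolled.
- **Consequence of use.** Protocol 10.6.5 makes this discretionary: "At Visit 2, any patient who has used medications restricted by the protocol may be discontinued from the study". If the patient is discontinued, Visit 3 procedures are to be done. The section assigns no efficacy outcome and gives no rule for use that comes to light at Visit 3. Protocol 10.3.4 lists restricted medication among reasons for which a patient may be removed.
- **Cure.** Protocol 11.6: "To be considered a Therapeutic Cure, the patient must have both Clinical and Mycological Cure of tinea pedis". Other medication plays no part in this definition.
- **Failure.** Besides clinical or mycological failure, Protocol 11.6 lists criterion (b), "the patient was considered to have an insufficient therapeutic response", and criterion (c), "the patient used topical drug therapy for irritation or pruritus on the feet after the treatment phase of the study". SAP 6 keeps the indication in (c) and states the window by visits: "the patient used topical drug therapy for irritation or pruritus on the feet between Visit 2" and Visit 3.
- **Populations.** The PP definition (Protocol 11.3.1, SAP 7) excludes patients with significant protocol deviations. The mITT definition (Protocol 11.3.2, SAP 7) has no such exclusion and does not mention restricted medication.
- **LOCF.** Patients discontinued early for reasons other than lack of effect enter the mITT with LOCF. Carry-forward from Visit 1 is spelled out for missing Visit 3 KOH or culture results.

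**The concern.** A non-study antifungal can produce both components of the primary endpoint, yet the plan's only medication rule concerns relief of irritation or pruritus. A patient cleared by a prohibited product can therefore be credited to the assigned arm in the mITT superiority analysis, which both active products must pass. Uncontrolled infection is a natural reason to use another antifungal, so use may be commoner on Placebo. That would raise the Placebo cure rate and shrink the difference under test. If the classification of these patients is not fixed in advance, it will be settled after their outcomes have been seen.

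**Working it through.** **1. Which rule applies to which patient (mITT)**

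Each patient below is in the mITT. Unless stated otherwise, the patient was not discontinued and has a clear score with negative KOH and culture at Visit 3.

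| Non-study medication | Rule reached | Scored as |
|---|---|---|
| Anti-itch topical on the feet after treatment | criterion (c) | Failure |
| Topical antifungal used for itch or irritation after treatment | criterion (c), which goes by indication | Failure |
| Topical antifungal directed at the infection, after treatment | none | Cure |
| Systemic antifungal, any time | none | Cure |
| Any antifungal during the treatment phase | none | Cure |
| Any antifungal outside (c), Visit 3 KOH or culture missing | LOCF from Visit 1 (positive by definition of the mITT) | Failure |
| Any antifungal, discontinued at Visit 2 | LOCF (11.3.2) or observed results (10.6.5) | not settled |

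Rows three to five are the definite gap. The last row is an ambiguity: KOH and culture are scheduled only at Visits 1 and 3, so carry-forward gives a failure, but 10.6.5 calls for Visit 3 procedures, which may yield negative results.

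**2. The plan's own power figure**

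Inputs (Protocol 11.2, SAP 5): Test 40%, Reference 45%, Placebo 10%; 216 per active arm and 108 on Placebo; two-sided 0.05; continuity-corrected Z-test with pooled standard error.

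Power = Φ[(d − cc − 1.96·SE0)/SE1], for Test against Placebo:

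- pooled rate = (216×0.40 + 108×0.10)/324 = 0.30
- SE0 = √[0.30×0.70×(1/216 + 1/108)] = 0.0540
- SE1 = √[0.40×0.60/216 + 0.10×0.90/108] = 0.0441
- cc = (1/216 + 1/108)/2 = 0.0069
- (0.30 − 0.0069 − 1.96×0.0540)/0.0441 = 4.25, so power is 0.99999

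The stated power of at least 99% is reproduced.

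**3. Effect of unclassified use (assumed rates)**

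The documents give neither a rate of use nor a clearance rate. Assume that a share u of Placebo patients are users, that a share c of them are clear at Visit 3, and that nobody on Test uses another antifungal. The Placebo rate is then 0.10(1 − u) + c·u.

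| u | c | Placebo rate | Test − Placebo | Power |
|---|---|---|---|---|
| 5% | 40% | 11.5% | 28.5 points | 99.99% |
| 5% | 50% | 12.0% | 28.0 points | 99.99% |
| 20% | 40% | 16.0% | 24.0 points | 99.5% |
| 20% | 50% | 18.0% | 22.0 points | 98.2% |

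For the last row, the pooled rate is 0.3267, SE0 0.0553 and SE1 0.0498. Then (0.22 − 0.0069 − 1.96×0.0553)/0.0498 = 2.10, so power is 0.982. Reference against Placebo in that row has power 99.9%.

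**4. Two checks on the assumptions**

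- *Equal use in both arms.* Let 20% of would-be failures use an antifungal and half of them clear. Test becomes 0.40 + 0.60×0.20×0.50 = 46%, Placebo 0.10 + 0.90×0.20×0.50 = 19%, and power is 99.9%.
- *Threshold.* With Test held at 40%, power drops below 99% at a Placebo rate of about 17.1%. That is (0.171 − 0.10)×108, or about 8 extra Placebo cures.

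**The case against.** A reader might infer that the plan fails users of anti-itch products but never users of antifungals. The text does not support that. Criterion (c) is defined by indication, not product class, so a topical antifungal used for itch or irritation after treatment already fails. Pruritus is the usual symptom of this disease (Protocol 8.1), so this covers part of the likely use.

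Other routes may fail further users. Criterion (b) could be applied to someone who needed another antifungal, and patients discontinued at Visit 2 may become failures through LOCF. These points narrow the gap without closing it. Criterion (b) is undefined, rests on judgement and is not tied to medication, so a patient who is clear at Visit 3 is an unlikely candidate. LOCF is not triggered for a patient who continues and has complete Visit 3 results.

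It can also be said that the bias works against the sponsor if use is commoner on Placebo, so it would not create a false superiority claim. That stands on that premise; it would favour an active product only if use were commoner there. PP equivalence is largely protected, though through the undefined term for significant deviations.

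Finally, keeping observed outcomes whatever else was used is a defensible analysis. But the plan already departs from it for anti-itch products, scoring those users as failures without LOCF. Failing every systemic antifungal user regardless of indication would go too far.

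**Conclusion.** The point holds for mITT patients who are not discontinued, who used a prohibited systemic antifungal, a topical antifungal directed at the infection, or either during the treatment phase, and who have observed clear results at Visit 3. As written, they are Therapeutic Cures. For users discontinued at Visit 2, the rules must be reconciled; the documents do not support saying that all medicated clearances count as cures.

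A reader might also infer that the superiority tests are at risk. They are not at the rates examined: Test-Placebo power runs from 99.99% down to 98.2%, below the stated 99% only at 20% Placebo-only use with 50% clearance. Those rates are assumptions. The case for change is correct classification of the primary endpoint in a test that the study must pass. It is worth fixing because the remedy is cheap.

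**What to change.** In SAP 6 and 7, recorded in SAP 8.7 and finalised before unblinding, state that in the mITT a patient is a Therapeutic Failure, with no LOCF and whether or not discontinued, if between first dose and Visit 3 the patient used:

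- a non-study topical antifungal on the feet, or
- a systemic antifungal for tinea pedis or another fungal infection of the feet.

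Systemic use for an unrelated indication is not failed automatically. Add a sensitivity analysis that keeps the observed outcomes of these patients. PP handling through review of significant deviations is unchanged, and so is every rule on patient care.

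**Cost.** A short scoring rule and one sensitivity analysis. No new data are needed: concomitant medication is reviewed at every visit, and listing L16.2.4.3 already has columns for treatment area, route, dates and indication. SAP 8.7 already records changes to protocol-defined populations, so there is a place for this one. A few observed clearances will be scored as failures. If users cluster on Placebo, the rule may favour the active products, which the sensitivity analysis would show.

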11.7 Efficacy Analysis

Therapeutic Equivalence

Therapeutic equivalence will be evaluated for the primary endpoint in the per-protocol (PP) population. If the 90% confidence interval (calculated using Yates' continuity correction) on the absolute difference between the proportion of patients with a Therapeutic Cure in the Test and Reference groups ($p_T - p_R$) is contained within the range [-20%, +20%] then therapeutic equivalence of the Test product to the Reference product will be considered to have been demonstrated.

The same statistical approach will be conducted for analyses of the secondary endpoints in the PP population.

CONFIDENTIAL PROTOCOL

A Randomized, Double-Blind, Vehicle-Controlled, Parallel-Design, Multiple-Site Clinical Study to Evaluate the Therapeutic Equivalence of Ketoconazole Cream 2% (Encube Ethicals Pvt Ltd) to Ketoconazole Cream 2% (G&W Laboratories Inc.) in the Treatment of Tinea Pedis

To declare therapeutic equivalence of the Test product to the Reference product, equivalence must be demonstrated for only the primary endpoint in the PP population.

Patients who are missing mycological culture data at the test-of-cure visit will not be included in the analysis for the secondary endpoint of Mycological Cure.

Superiority to Placebo

Superiority of the Test and Reference products against the Placebo product for the primary endpoint will be evaluated in the mITT population using, if necessary, LOCF as described in section 11.3.2. If the proportions of patients with a Therapeutic Cure in the Test and the Reference product groups are numerically and statistically superior to that of the Placebo ($p < 0.05$; using a two-sided Cochran-Mantel-Haenszel [CMH] test, stratified by clinical site) then superiority of the Test and Reference products over Placebo will be concluded.

The same statistical approach will be conducted for analyses of the secondary endpoints in the mITT population.

To declare superiority of the Test and Reference products over Placebo, their superiority must be demonstrated for only the primary endpoint in the mITT population.

Treatment-by-Site Interaction and Pooling of Clinical Sites

As this is a multiple-site study, the interaction of treatment-by-site may be evaluated for the primary efficacy endpoint in the PP population for equivalence testing. The treatment-by-site interaction will be evaluated by the Breslow-Day test for homogeneity of the odds ratio at the 5% significance level ($p < 0.05$, 2-sided). A site(s) with a low enrollment rate(s) may be pooled with its geographically closest site, so as to avoid bias in the stratification of the sites in the CMH test and in the estimation of a treatment-by-site interaction effect. The pooling will be done for low enrolling sites that account for less than 4-7% of the total number of patients in the PP population at the site with the highest enrolling rate in the PP population. If the treatment-by-site interaction term is found to be statistically significant ($p < 0.05$) for the primary endpoint, then the interaction term will also be assessed for clinical relevance before pooling the data across sites. This will include examination of Therapeutic Cure rates at each site where sample sizes per treatment may be influential in the assessment of the interaction. The treatment-by-site interaction may also be evaluated for the analyses of the secondary endpoints in the PP population for equivalence testing if the treatment-by-site interaction is found to be significant in the primary analysis.

11.8 Safety Analysis

Adverse events (AEs) will be classified using standard Medical Dictionary for Regulatory Activities (MedDRA) terminology Version 21.0 or higher and summarized by treatment group. Summary tables comparing the type, date of onset, date of resolution, incidence, severity, relationship to the study product, outcome, and action taken will be prepared by treatment group. If sufficient data exist, then AE frequencies will be compared among the three treatments using Fisher's exact test; if this test is statistically significant at the 5% significance level, then a pairwise Fisher's exact test comparing Test and Reference will be conducted.

CONFIDENTIAL PROTOCOL

A Randomized, Double-Blind, Vehicle-Controlled, Parallel-Design, Multiple-Site Clinical Study to Evaluate the Therapeutic Equivalence of Ketoconazole Cream 2% (Encube Ethicals Pvt Ltd) to Ketoconazole Cream 2% (G&W Laboratories Inc.) in the Treatment of Tinea Pedis

Signs and symptoms of tinea pedis will not be considered AEs, unless in the Investigator's opinion, they have increased in frequency and/or severity to such an extent that the Investigator/patient considers that it is in the patient's best interest to be discontinued from further participation in the study and given alternative therapy for their condition.

Concomitant medication use will be tabulated by patient.

12.0 REGULATORY OBLIGATIONS

12.1 Institutional Review Board

The study protocol, ICF, Investigator's Brochure, or package insert (as applicable), and any specific advertising will be submitted to and approved by an IRB before the start of the study. A form must be signed by the chairman or designee of the IRB noting the approvals. This notification of the board's approval along with a description by profession and gender of the board's composition will be provided to the Sponsor.

12.2 Study Documentation

This study will be conducted in compliance with the protocol; GCPs and all applicable regulations, including the Federal Food, Drug, and Cosmetics Act, US applicable Code of Federal Regulations (title 21), parts 50, 56, 312, 320, and any IRB requirements relative to clinical studies; and the Declaration of Helsinki, June 1964, as modified by the 64th World Medical Association General Assembly, October 2013.^{10,18-20} The Investigator will permit trial-related monitoring, audits, IRB review, and regulatory inspections providing direct access to source data/documents.

12.2.1 Protocol

The Investigator indicated on FDA Form 1572 will act as the Principal Investigator at each study site. Protocols will be noted as approved by placement of the Novum Representative's signature on the cover page. The Sponsor of the study will also approve the protocol by having a study-responsible individual sign the protocol cover page. The Principal Investigator will sign the protocol signature page indicating their agreement to conduct the study according to the protocol.

12.2.2 Informed Consent

An ICF that includes all of the relevant elements currently required by FDA and local state regulations will be provided to each prospective patient before enrollment into the study. The type and method of study, tests to be administered, any potential or possible hazards, and the patient's right to withdraw from the study at any time will be explained to the patients by the Investigator or designee. Once the Investigator or designee is assured that an individual candidate understands the implications of participating in this study, the patient will be asked to give consent by signing and dating in the appropriate areas of the ICF. The Investigator or designee will also sign and date the form, along with a staff member who will sign the ICF as a witness to verify that the patient has indeed received information. If any other language is required, translation will be performed by a certified translator. A copy of the ICF and Assent (when applicable) will be provided to the patient.

CONFIDENTIAL PROTOCOL

A Randomized, Double-Blind, Vehicle-Controlled, Parallel-Design, Multiple-Site Clinical Study to Evaluate the Therapeutic Equivalence of Ketoconazole Cream 2% (Encube Ethicals Pvt Ltd) to Ketoconazole Cream 2% (G&W Laboratories Inc.) in the Treatment of Tinea Pedis

12.2.3 Protocol and Informed Consent Changes

Sponsor approved changes to the protocol or the ICF form will be implemented as revisions to the original documents and will require additional review and approval by the IRB. Revisions to the original protocol will be documented in amendments, incorporated as a preface to the new version. Any revision that substantially alters the study design or increases potential risk to the patient requires the patient's consent to continue in the study. The approvals will be processed in accordance with the established IRB procedures. Copies of all protocol and ICF amendments/revisions, along with letters noting IRB approval, will be submitted to the Sponsor.

